4 STUDY PLAN

4.1 Study Design

This is a non-randomized, prospective, open-label implementation study to determine the feasibility of establishing and integrating a PGx test into clinical care. The effectiveness aims will be assessed by comparing toxicity outcomes using a historical control group without clinical genotyping. The implementation will be deployed across cancer care sites within Penn medicine in sequential fashion, starting with PCAM followed by PPMC, and LGH.

Patients with a GI malignancy initiating chemotherapy with a fluoropyrimidine (5-FU or capecitabine) and/or irinotecan will be consented to undergo *DYPD* and *UGT1A1* genotyping, the study intervention. The PGx test order will be placed by the research coordinator and signed by the medical oncologist; a blood sample will be obtained by the phlebotomist, or saliva self-collected by the patient in clinic, and sent to CAG for genotyping. Results will be returned in the Precision Medicine tab in PennChart. For patients with an actionable genotype (variants that would require a dose adjustment of 5-FU, capecitabine or irinotecan), clinical decision support (CDS) tools will alert the ordering oncologist of the PGx result and the recommended dose adjustment. The prescribing oncologist will ultimately decide the chemotherapy dose incorporating clinical and genetic factors. The efficacy and safety of this PGx-guided approach will be determined by comparing the incidence of severe treatment related adverse events to a historical control group of GI cancer patients enrolled into PMBB.

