7.4 Baseline clinical data collection

The following information will be obtained at screening and from the patient medical record if performed as part of usual care and available in the medical record:

- Signed informed consent form
- Inclusion and exclusion criteria
- Demographic data: age, gender, race/ethnicity
- Cancer history: GI tumor type, stage, previous cancer treatments, number of lines of therapy
- Routine physical examination: ECOG performance status (see Appendix 14.2), height (cm), weight (kg)
- Vital signs: heart rate, blood pressure
- Hematology: hemoglobin, hematocrit, white blood cell count, ANC, neutrophils, eosinophils, basophils, lymphocytes, monocytes, platelets

- Clinical chemistry: sodium, potassium, calcium, glucose, creatinine, BUN, AST, ALT, alkaline phosphatase, total bilirubin, albumin
- Creatinine clearance (using Cockcroft-Gault formula)
- Concomitant medications (including dose, unit, frequency, route of administration and indication)

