8.2 Overview of statistical methods

Descriptive statistics (mean, SD, median, interquartile range, range, counts, and percentage) will be used to describe and compare (t-test or rank sum test for continuous variables and Fisher's exact test for categorical variables) baseline characteristics between the historical control group and PGx arms.

8.2.1 Implementation Endpoint(s):

- We will report the number and proportion of tests returned prior to the first dose of chemotherapy.
- We will report the proportion of dose modifications made in agreement with genotype-guided dosing recommendations at the first dose.
- The proportion of tests ordered compared to the number eligible for testing.

8.2.2 Secondary Endpoint(s):

1. Clinical endpoints

- a. The proportion of patients experiencing severe TRAEs will be compared in the PMBB historical control group vs. the PGx group using Fisher's exact test.

Subgroup analyses will be performed by tumor type.

- b. The relative dose intensity (RDI) will be calculated for 5-FU, capecitabine or irinotecan as the cumulative administered dose divided by the anticipated cumulative dose over the first 6 cycles. RDI will be compared in the PMBB historical control group vs. the PGx group using linear regression adjusted for sex, race, BMI, tumor type, cancer stage, line of therapy and ECOG performance status.

Subgroup analyses will be performed by tumor type.

2. Patient reported outcomes

Patient reported outcomes as assessed on a Likert scale will be reported as means (SD) and compared between the PMBB historical control group vs. the PGx group using linear regression adjusting for age, sex, race, tumor type, cancer stage, BMI, line of therapy, and ECOG performance status.

3. Patient attitudes toward PGx testing

Patient knowledge and attitudes towards PGx testing will be assessed on a Likert scale will be reported as means (SD). We will compare results by sex, race, tumor type, and insurance status by using linear regression. (See survey in Appendix 14.7)

8.2.3 Tertiary Endpoint(s):

1. Clinical endpoints in minority populations

The proportion of patients experiencing severe TRAEs will be compared in the PMBB historical control group vs. the PGx group using Fisher's exact tests, stratified by race.

2. Minor allele frequencies will be reported by ancestry for the DPYD and UGT1A1 genes.
3. Medical services utilization and costs

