We will obtain data from Data Analytics Center (DAC) on service utilization and costs. These will include: number of physician visits; number of emergency department visits; number of hospitalizations; length of hospital stay; number of emergency department and hospital admissions associated with drug-related adverse events; DPYD and UGT1A1

genetic testing costs; physician visit cost; emergency department visit costs; hospitalization costs; inpatient and physician-administered medication costs; and total costs. Care Everywhere will be utilized to obtain information if patients received care outside Penn Medicine. Additionally, medical records will be requested for admissions that occur outside of Penn Medicine.

We will compare utilization and costs incurred by the PMBB usual care group with utilization and costs incurred by the PGx group using Poisson regression methods (for number of visits), and linear regression methods with appropriate transformations (e.g., log-transform, winsorization) to account for skewness in utilization and cost distributions.

4. Survival Analysis

Overall survival and progression free survival at approximately six months will be compared between the PMBB historical control group vs. the PGx group by use of Kaplan-Meier estimators and log-rank tests. Cox proportional regression analysis will be performed to adjust for clinical covariates including age, sex, race, tumor type, cancer stage, BMI, and ECOG performance status.

5. Pre-treatment uracil and fluoropyrimidine associated toxicity

First, we will examine the range of pre-treatment uracil concentrations with the association of severe toxicity to determine if there is a cut-off whereby toxicity occurs. Previous studies have proposed uracil $> 16\text{g/ml}$ as highly predictive for severe toxicity, but we will validate this cut-off in our patient population.¹⁵ We will also examine whether the pre-treatment uracil levels vary in *DPYD* variant carriers. Second, we use logistic regression models to determine the risk of severe toxicity including a binary factor for uracil concentration (above and below cut-off), with adjustment for age, sex and treatment regimen.

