Adherence and protocol deviations	17	
 Removal of inclusion criteria of ECOG status, patients with higher ECOG status (3 or 4) still suitable for treatment with fluoropyrimidines. Oncologist will determine suitability for treatment with fluoropyrimidines on a case-by-case basis. Removal of inclusion criteria of prior treatment of fluoropyrimidines, physicians have expressed interest in obtaining genotype information regardless of a patient's prior treatment status, and particularly for individuals with previous intolerance of fluoropyrimidine to guide future treatment decisions. Participants that received the PGx test after initiation of chemotherapy, due to requests by the treating oncologist, were not included as part of the primary analysis and were reported/described separately and noted as protocol deviations. Updated timeframe for endpoint collection, feasibility endpoint time frame revised from '7 days' to 'prior to the first dose of chemotherapy'. Seven days is less clinically relevant than patient-specific treatment schedules. adverse event data and PRO questionnaires to be collected over first six cycles, not months. It is not necessary to collect AE data over the longer time period for study purposes given that chemotherapy toxicity is typically experienced during initial cycles. Prospective completion of chemotherapy related toxicity per the National Cancer Institute-Common Terminology Criteria for Adverse Events (NCI-CTCAE) was not feasible due to a lack of a consistent research coordinator throughout the study. In addition, the completion rate for the PROs was very low (22%) therefore we could not assign a grade to the adverse event. Revised definition severe toxicities from \geq Grade 3 toxicities to treatment related adverse events requiring treatment in the hospital, emergency department, or oncology evaluation center.

Analysis population	18	Modified intent to treat, removing participants that did not meet the inclusion criteria (i.e., received PGx test after chemotherapy or did not receive qualifying chemotherapy agent).
---------------------	----	---

Section 5: Trial population

Section	Index	Description

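### The Cox model for PFS and OS against historical controls does not name line of therapy, although the RDI and PRO models for the same comparison do

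*Combined protocol and SAP*

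**What the plan says.** Protocol section 8.2.3, item 4 states: "Overall survival and progression free survival at approximately six months will be compared between the PMBB historical control group vs. the PGx group". The methods are Kaplan-Meier curves and log-rank tests, followed by a Cox model to "adjust for clinical covariates including age, sex, race, tumor type, cancer stage, BMI, and ECOG performance status".

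Two other protocol models with a named covariate list compare the same cohorts, both in section 8.2.2:

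- RDI: "linear regression adjusted for sex, race, BMI, tumor type, cancer stage, line of therapy and ECOG performance status".
- PROs: "linear regression adjusting for age, sex, race, tumor type, cancer stage, BMI, line of therapy, and ECOG performance status".

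The variable is collected. The cancer history in section 7.4 includes "previous cancer treatments, number of lines of therapy", and SAP item 25 repeats it.

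The control is historical (section 4.1): "The effectiveness aims will be assessed by comparing toxicity outcomes using a historical control group without clinical genotyping". Section 5.2 excludes prior irinotecan but not prior fluoropyrimidine. SAP item 17 records the change: "Removal of inclusion criteria of prior treatment of fluoropyrimidines". The amendment history dates it to version 4.0, November 10, 2021. SAP item 12 puts recruitment at March 2021 to December 2022. Section 7.5 times both OS and PFS from treatment initiation.

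The SAP contains no Cox model and no PFS analysis. Item 29b says only that one-year OS was reported for the two cohorts.

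**The concern.** In a non-randomized comparison, the adjustment set is the main protection against case-mix differences. A patient starting a later line of treatment is usually further along in the disease than one starting first-line treatment, and here the survival clock starts at treatment initiation for both. If one cohort holds more later-line patients, its hazard is higher for reasons unrelated to genotype-guided dosing.

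The prospective cohort can mix lines, and could do so more readily once fluoropyrimidine-pretreated patients became eligible partway through recruitment. Nothing in the documents fixes or matches the line mix of the PMBB controls.

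At stake is how the survival result is read. Section 10.2.1 says the effect on oncologic outcomes is unknown. A hazard ratio shifted by line mix could suggest that genotype-guided dosing costs survival, or could hide such a cost.

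**Working it through.** **Step 1. Compare the covariate lists.** The documents state no hazard ratio, event count or power for PFS or OS, so there is no survival figure to reproduce. The check is of the lists themselves.

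| Model | Compares PGx with PMBB? | Line of therapy named? |
|---|---|---|
| RDI, 8.2.2 item 1b | yes | yes |
| PRO, 8.2.2 item 2 | yes | yes |
| Cox PFS/OS, 8.2.3 item 4 | yes | no |
| Uracil logistic, 8.2.3 item 5 | no | no |
| Logistic model for severe treatment-related adverse events, SAP item 27, 2c | cohort not listed as a term | no |

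The Cox list is the PRO list with one item removed: line of therapy. No reason is given.

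**Step 2. Illustrate the bias.** None of these inputs is in the documents; all are assumptions. Later-line shares are p1 and p0 in the two cohorts. Later line carries hazard ratio g against first line. There is no true cohort effect, and cohort is the only model term. At the start of follow-up, the ratio of average hazards is

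HR ≈ [1 + p1(g − 1)] / [1 + p0(g − 1)].

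With p1 = 30% and p0 = 10%:

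- g = 1.5: 1.15 / 1.05 = 1.095
- g = 2.0: 1.30 / 1.10 = 1.182
- g = 2.5: 1.45 / 1.15 = 1.261

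The fitted Cox value is a little lower at the larger g, because later-line patients fail sooner and leave the risk set. Simulation used 500 per cohort, exponential survival with a first-line median of 14 months, uniform censoring at 4 to 8 months and 300 runs per setting. It gave 1.086, 1.157 and 1.227. With line added to the model, it gave 0.993, 0.989 and 0.993.

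**Step 3. Vary the assumptions.**

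- *Direction.* Reversing the shares inverts the formula: 1/1.095 = 0.91, 1/1.182 = 0.85 and 1/1.261 = 0.79.
- *Similar shares.* With 20% and 15%, the formula gives 1.10/1.075 = 1.02, 1.20/1.15 = 1.04 and 1.30/1.225 = 1.06. With equal shares it gives exactly 1.
- *Absorption by a named covariate.* If the 10% versus 30% imbalance arises wholly from a stage imbalance and stage is in the model, simulation gives 1.01, 1.00 and 1.00. This is a favorable case, because any imbalance in line within stage would remain.

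**The case against.** The strongest reply has four parts.

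1. *The list is open.* The word *including* lets the analyst add line of therapy, so a reader who infers that the protocol bars it goes too far. This stands. It does not cure the gap, because an analysis that fits only the seven named covariates would still follow the plan.

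2. *The illustration is not the planned model.* Its fit has cohort alone, whereas the protocol adjusts for stage, tumor type and ECOG, which may carry much of the line effect. This stands. A reader might take 1.09 to 1.23, or an inflated false-positive rate derived from it, as the bias of this trial's analysis. The documents do not support that, because line mix, event rates and the effect of line are all unstated.

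3. *The analysis carries limited weight.* Section 3 lists PFS and OS as tertiary, and the SAP drops the Cox model. By section 8.1 only about 10% of patients carry actionable genotypes, so a whole-cohort hazard ratio says little about dose reduction in any case. This stands and limits the importance of the point. But one-year OS set side by side with no stated adjustment leaves the same confounding in place.

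4. *Imbalance would be seen.* Section 8.2 compares baseline characteristics between cohorts, and number of lines is a baseline item. Seeing an imbalance does not adjust for it.

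Three further inferences fail. Survival is not the only efficacy information, since section 7.5 also collects tumor response. Line is not the only case-mix factor missing from the Cox list: presence of metastases and treatment intent, used in SAP item 27, are absent too. And not every other adjusted model names line; the table shows two that do not.

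**Conclusion.** The point holds as a gap in prespecification. The survival model omits by name a covariate that the protocol's own RDI and PRO models treat as needed for the same non-randomized comparison, and which the study collects. If the line mix differs between cohorts beyond what stage, tumor type and ECOG explain, the hazard ratio is biased, in a direction set by which cohort has more later-line patients.

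The size is unknown. The illustrative 1.09 to 1.23 rests on a 20-point difference in later-line share, a later-line hazard ratio of 1.5 to 2.5 and no other adjustment. It falls to about 1.02 to 1.06 with a 5-point difference, and to about 1.0 with equal shares or full absorption by a named covariate. The documents do not show that an imbalance exists, only that nothing in the named model guards against it directly.

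**What to change.** In protocol section 8.2.3, item 4, add line of therapy (first versus later) to the Cox model as a covariate or stratum. Tabulate it by cohort with the other baseline characteristics. Apply the same adjustment to any between-cohort survival comparison made under SAP item 29b. Reconcile the two documents: the protocol plans Cox models for PFS and OS at about six months, while the SAP reports one-year OS only. State which applies and why.

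The cost is one more model term. Line must also be abstracted for the PMBB controls, whose data capture the documents do not describe, but the protocol's RDI and PRO models already require it.

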4.4 Dose Adjustments based on Genotype

Genotype-guided dose recommendations will be made according to peer-reviewed, evidence-based clinical guidelines from the NIH-funded Clinical Pharmacogenetics Implementation Consortium (CPIC) for 5-FU and capecitabine and the Dutch Pharmacogenetics Working Group (DPWG) for irinotecan (refer to Tables 2 and 3).^{3,12}

Table 2. Genotype-guided dosing recommendations

Drug(s)	Gene	Genotype	Gene Activity Score*	Phenotype	Clinical Implication	Dose Recommendation
5-FU, capecitabine	DYPD	See Table 3 below	2	Normal Metabolizer	Patient is predicted to have a normal risk of toxicity when treated with 5-FU or capecitabine.	Initiate 5-FU or capecitabine at the standard dose.
			1.5	Intermediate Metabolizer	Patient is predicted to have an increased risk of severe toxicity when treated with 5-FU or capecitabine.	Reduce starting dose by 50% followed by dose titration based on toxicity. 5-FU Bolus: if standard dose is 400 mg/m ² , consider 200 mg /m ² 5-FU CIV: If standard dose is 2400 mg/m ² , consider 1200 mg/m ² Capecitabine: If standard dose is 1000-1250 mg/m ² , consider 500-625 mg/m ²

		1	Intermediate Metabolizer	Patient is predicted to have an increased risk of severe toxicity when treated with 5-FU or capecitabine.	
Reduce starting dose by 50% followed by dose titration based on toxicity.
 
5-FU Bolus: if standard dose is 400 mg/m², consider 200 mg /m²
 
5-FU CIV: If standard dose is 2400 mg/m², consider 1200 mg/m²
 
Capecitabine: If standard dose is 1000-1250 mg/m², consider 500-625 mg/m²
	
		0.5	Poor Metabolizer	Patient is predicted to have an increased risk of severe toxicity when treated with 5-FU or capecitabine.	
Avoid use of 5-FU or capecitabine-based regimens. If alternative agents not considered a suitable option, 5-FU should be administered at a strongly reduced dose (i.e. <25% of normal starting dose) with early therapeutic drug monitoring.
	
		0	Poor metabolizer	Patient is predicted to have an increased risk of severe toxicity when treated with 5-FU or capecitabine.	
Avoid use of 5-FU or capecitabine-based regimens.
	
Irinotecan, Liposomal irinotecan	UGT1A1	*1/*1	N/A	Normal Metabolizer	Patient is predicted to have a normal risk of toxicity when treated with irinotecan.	Initiate irinotecan at the standard dose.

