10.8.3 Protocol Deviations

The PI and the study team should document all scenarios where the protocol is not followed and provide, in particular:

- Who deviated from the protocol
- What was the deviation
- When did the deviation occur
- How did the deviation happen
- What is the impact of the deviation
- A root cause analysis of why the deviation occurred

Not following the genotype guided dose recommendation is NOT considered a protocol deviation, but will be recorded as one of the study outcomes.

If the assessment results in a determination that any of the following are potentially affected, the deviation would be considered of significant impact:

- having the potential to adversely affect subject safety; OR

- increases risks to participants; OR
- adversely affects the integrity of the data; OR
- violates the rights and welfare of participants, OR
- affects the subject's willingness to participate in research.
- there is a potential for an overall impact on the research that should be shared with the IRB for consideration and development of next best steps to address it

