		5. To determine if providing PGx test results will improve patient reported outcomes (PRO) during the first six cycles of chemotherapy.
Hypothesis	9	Providing clinicians with the ability to order a PGx test with a rapid turnaround time for results, along with specific dosing recommendations, will increase the utilization of PGx tests to guide pharmacotherapy decisions and improve patient drug related outcomes.

Section 3: Study Methods

Section	Index	Description
Trial design	10	Non-randomized, prospective, open-label implementation study to determine the feasibility of establishing and integrating a PGx test into clinical care.
Randomization	11	n/a
Sample size	12	No sample size calculation was performed for this feasibility study with pragmatic inclusion of eligible participants recruited over a 20- month period (Mar 2021- Dec 2022).
Interim analyses	13	No interim analyses planned
Timing of final analysis	14	Participants were followed until May 31, 2023, for toxicity assessments with an intention of 6-month follow-up for each participant. All analyses were performed collectively in May-June of 2024.
Timing of outcome assessments	15	Serial questionnaires assessing patient reported outcomes (PROs) for symptoms associated with to adverse events will be prospectively collected by the study team at the time of each treatment for the first 6 cycles.

Section 4: Statistical Principles

Section	Index	Description
Confidence intervals and p-value	16	
No hypothesis testing was performed for the primary outcome (feasibility) or secondary implementation outcomes (fidelity, penetrance).
 
Descriptive statistics (mean, SD, median, interquartile range, range, counts, and percentage) will be used to describe and compare (t-test or rank sum test for continuous variables and Fisher's exact test for categorical variables) baseline characteristics between the historical control group and PGx arms.
 
For the effectiveness aims, significance was set at an alpha=0.05.
 
No corrections were made for multiple testing. Confidence intervals pertaining to the odds of experiencing a severe TRAE were reported.

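### Section 8.2.3 does not fix which uracil cut-off enters the logistic model, and the model names neither DPYD genotype nor starting dose as a covariate

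*Combined protocol and SAP*

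**What the plan says.** Protocol Section 8.2.3, item 5, sets out two steps. The first relates uracil concentrations to severe toxicity "to determine if there is a cut-off whereby toxicity occurs". The same paragraph cites an earlier proposal of 16 as highly predictive and adds "but we will validate this cut-off in our patient population". It continues: "We will also examine whether the pre-treatment uracil levels vary in" DPYD variant carriers. The second step is a logistic model for severe toxicity, "including a binary factor for uracil concentration (above and below cut-off), with adjustment for age, sex and treatment regimen".

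The plan gives no rule for choosing a cut-off, and no hold-out sample, resampling or corrected p-value. The SAP does not mention uracil. For the effectiveness aims, SAP Section 4 says "For the effectiveness aims, significance was set at an alpha=0.05" and then "No corrections were made for multiple testing". By contrast, protocol Section 8.3 applies a 5% false discovery rate to the microbiome substudy.

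On dose, Table 2 in Section 4.4 recommends for DPYD intermediate metabolizers: "Reduce starting dose by 50% followed by dose titration based on toxicity". Section 10.8.3 adds: "Not following the genotype guided dose recommendation is NOT considered a protocol deviation". The dose given can therefore differ from what genotype implies.

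**The concern.** The cut-off in the second step could be the published value or the one found in the first step. These are different analyses. A threshold fixed beforehand gives an ordinary test. A threshold picked because it separates toxic from non-toxic patients, then tested in those same patients, gives a p-value that is too small and an odds ratio too far from 1. The write-up would read the same either way.

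The second issue is the covariate list. If carriers tend to have high uracil, which the plan itself intends to examine, they are also the patients whose first dose is most likely to be lowered. Tertiary objective 5 in Section 3 concerns toxicity with the first dose, which is the dose that genotype changes. A model without genotype or dose mixes the effect of uracil with the effect of the intervention. At stake is whether the study can say anything dependable about a proposed toxicity threshold.

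**Working it through.** The documents give no sample size, power or error rate for the uracil analysis, so there is no stated figure to reproduce.

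**Inputs from the protocol.** Uracil is measured at PCAM only (7.7), where Table 4 plans 240 participants, if the patient is willing (7.7) and if time and resources permit (4.5). Severe fluoropyrimidine toxicity is up to 30% (2.2). The published uracil odds ratio is 5.3 (2.2). Toxicity was 39% at standard dose against 23% in dose-reduced carriers (2.2). The effectiveness hypothesis is 60% falling to 30% (8.1).

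**Assumptions.** 60-240 samples; toxicity 10-30%; two-sided alpha 0.05, borrowed from the effectiveness aims; 90% adherence to the dose recommendation; 30-50% of carriers and 5-10% of non-carriers above the cut-off.

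**1. Cut-off chosen and tested in the same patients, with no true association.** For each simulated dataset (10,000 per setting), the 2x2 score chi-square was computed at the chosen cut-off and compared with 3.841. For a single binary predictor this is the logistic score test; covariates were left out.

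| How the cut-off is set | False-positive rate at nominal 5% |
|---|---|
| Smallest p-value, central 80% of uracil values | 35-44% |
| Smallest p-value, central 50% | 23-29% |
| One-directional Youden index, either range | 11-20% |
| Fixed beforehand (80th or 90th percentile) | 3.6-5.5% |
| Chosen in one half, tested in the other (N = 120, 240) | 4.6%, 4.9% |

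For the smallest-p search, the median selected odds ratio, in whichever direction, is 1.6-5.0 when the truth is 1. To hold a true 5% with a central-80% search, the chi-square must exceed about 8.6-8.9, a nominal p of about 0.003 (N = 120-240, toxicity 30%).

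**2. Genotype and dose omitted.**

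- Carrier frequency: 3-5% partial deficiency in people of European ancestry (2.2); 4% was used as the lower value. From Table 1, the DPYD allele frequencies sum to 0.0372 (European) and 0.021 (African). Then 1 - (1 - 0.0372)² = 7.3% and 1 - (1 - 0.021)² = 4.2%. With the 20% African ancestry in Section 5.4: 0.8 × 7.3% + 0.2 × 4.2% = 6.7%.
- Expected carriers: 60 × 0.04 = 2.4 up to 240 × 0.067 = 16.1.
- Odds ratio for dose reduction: (0.23/0.77)/(0.39/0.61) = 0.47; under the 60% to 30% hypothesis, (0.30/0.70)/(0.60/0.40) = 0.29.

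Worked case: carriers 6.7%, of whom 50% have high uracil; 5% of non-carriers high; reference risk 25%; true odds ratio 5.3; dose odds ratio 0.47.

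- Carriers among high-uracil patients: 0.0335/(0.0335 + 0.0467) = 42%; at reduced dose, 0.9 × 42% = 38%.
- High-uracil risk: full dose, odds 5.3/3 = 1.77, risk 0.639; reduced dose, odds 0.825, risk 0.452. Mixture: 0.62 × 0.639 + 0.38 × 0.452 = 0.568, odds 1.317.
- Low-uracil risk: 3.3% are at reduced dose, so the mixture is 0.246, odds 0.327.
- Observed odds ratio: 1.317/0.327 = 4.03.

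| Scenario set | True 5.3 appears as | True 1 appears as |
|---|---|---|
| Dose odds ratio 0.47 | 4.0-4.7 | 0.80-0.92 |
| Dose odds ratio 0.29 | 3.4-4.4 | 0.72-0.89 |
| 0.47, with genotype odds ratio 1/0.47 = 2.14 | 5.35-5.43 | 1.01-1.03 |

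In the last row, dose reduction just cancels the extra genotype risk, and the distortion is 1-3%.

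**The case against.** The best defence is that the paragraph names 16 and promises to validate it, so the binary factor may simply be that value. If so, the search problem disappears. A reader might infer that the plan commits to a data-derived cut-off and that the test is therefore invalid. The text does not support that; it leaves the choice open. What stands is the ambiguity, since the model's cut-off follows a step whose stated purpose is to look for one.

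The upper error rates also assume an extensive p-value search that the plan does not describe. That is fair, and the range is given for that reason. Its lower end is still about twice nominal.

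On dose, a reader might infer that the omission masks the association. Cutting 5.3 to 3.7-2.5 would require dose reduction to remove all excess risk in 25-50% of high-uracil patients, from a 20% baseline. The documents support neither assumption. With the 39% against 23% that Section 2.2 cites, the same mix gives 4.4-3.6, which is attenuation, not masking.

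Checking a decision threshold does need a binary analysis, so dichotomising is not wrong in itself. Adjustment also has limits. With 2-16 carriers it will be imprecise, and dose partly reflects clinical judgment, so adjusting for dose alone can bring in confounding by indication. Finally, this is a tertiary, single-site analysis with no power claim. These points limit the weight of the concern but do not remove it.

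**Conclusion.** The concern holds in a conditional form. The plan permits, but does not require, testing a searched cut-off in the patients who supplied it. If that happens, the false-positive rate is about 2 to 9 times nominal and the odds ratio is exaggerated. If 16 is fixed beforehand, the test is sound on this point.

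Leaving out genotype and dose is a separate and smaller defect. In the scenarios without a direct genotype effect, a true 5.3 is understated by about 11-36%; if dose reduction offsets genotype risk, the bias is close to nil. The two biases run in opposite directions, but it would go too far to conclude that no result could be interpreted: with a fixed cut-off, only the modest dose bias remains.

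These sizes rest on the assumed sample count, uracil distribution by carrier status, adherence and reference risk, none of which the documents give. The omission of uracil from the SAP means that nothing there settles either question.

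**What to change.** In Section 8.2.3, and in a matching new SAP entry:

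- State that the binary test uses only the published cut-off. Confirm its unit, which reads g/ml in the available text and may have lost a character in conversion.
- Make log uracil, as a single continuous term, the main association analysis. Add no spline unless events allow: the assumed ranges give from 60 × 0.10 = 6 to 240 × 0.30 = 72 events.
- Label any data-derived cut-off exploratory, with cross-validation, bootstrap optimism correction or a p-value for a maximally selected statistic.
- Add DPYD carrier status and/or first dose as a percentage of standard as a covariate, preferably not dose alone, with a sensitivity analysis in non-carriers.
- Reconcile the outcome. Section 3 specifies Grade 3 to 5 toxicity with the first dose, whereas Section 7.5 defines severe events by care setting and Appendix 14.3 says grading has stopped.

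The cost is some added text and analysis, and less precise estimates in a small sample. Genotype comes from the study test, and doses are already due for collection where available (Sections 7.3 and 7.5). The SAP dates its analyses to May-June 2024; if the uracil model has already been run, re-analysis and relabelling need no new data collection beyond this.
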